8 EXPLORATORY EFFICACY

Measures of efficacy will be based on Investigator assessments of ACC and flare. [REDACTED]

[REDACTED]

[REDACTED]

8.1 EFFICACY VARIABLES

Efficacy of TRS01 will be assessed by evaluation of anterior chamber inflammation by Investigator assessment with slit-lamp biomicroscopy. [REDACTED]

[REDACTED]

Slit-lamp biomicroscopy of the both eyes will be used to examine eye structures at each study visit. At Day 1/Visit 3 (1-day post-surgery), slit-lamp biomicroscopy will be performed prior to IP administration. Areas assessed will include lids, conjunctiva, cornea, anterior chamber cells and flare, iris, pupil, lashes, ocular motility, lens and cataract status.

[figure not shown]
8.1.1 Anterior Chamber Cells

Note: The same investigator must assess and score anterior chamber cells and flare at Visit 3, Visit 4, Visit 5 and Visit 6 for an individual subject.

8.1.1.1 Slit-lamp biomicroscopy

At each visit, slit-lamp biomicroscopy under halogen illumination system will be performed by the Investigator on both eyes to assess ACC.

The following scoring scale for anterior chamber cells will be used:

8.1.2 Flare

The level of flare in the anterior chamber will be assessed by the Investigator at each study visit for both eyes, using slit-lamp biomicroscopy and recorded according to the following scale:

- 0 = None

- 1 = Mild (trace to clearly noticeable, visible)
- 2 = Moderate (without plastic aqueous humor)
- 3 = Marked (with plastic aqueous humor)
- 4 = Severe (with fibrin deposits and/or clots)

8.1.3 Subject-Rated Ocular Pain Assessment

In the clinic, subjects will be handed a laminated card on which is printed the Subject-Rated Ocular Pain Assessment. Each subject will be asked to subjectively rate their pain at Visit 3 to 6 based on this scale. This information will be provided to study personnel to enter into the subject's source documentation.

The grading scale for pain to be used will be as follows:

0 = None: Absence of pain.

1 = Minimal: Presence of mild sensation or discomfort typical of post cataract surgery (e.g., diffuse or focal foreign body sensation, mild transient burning or stinging, etc.)

2 = Mild: Mild, tolerable aching of the eye.

3 = Moderate: Moderate or more prolonged aching sufficient to have desire to use over the counter (OTC) analgesics (e.g. acetaminophen).

4 = Moderately Severe: More prolonged aching requiring the use of an OTC analgesic other than acetaminophen.

5 = Severe: Aching or throbbing pain that is not tolerable (e.g. constant or nearly constant sharp stabbing pain, throbbing or aching, etc.) requiring prescription analgesics.

9 STATISTICS

9.1 STATISTICAL METHODS

Continuous measures (e.g., age) will be summarized descriptively by the mean, standard deviation, median, minimum and maximum values. Categorical measures will be summarized by the number and percent of subjects. The statistical analyses will be performed in accordance with the Statistical Analysis Plan. All study data will be listed by treatment, subject and visit (as applicable).

9.1.1 Subject Disposition, Demographic and Background Characteristics

Subject disposition, demographic characteristics, and background variables will be summarized by treatment group.

9.1.2 Analysis of Safety

Analysis of safety data will be presented for all subjects. AEs will be coded using Medical Dictionary for Regulatory Activities (MedDRA, most current version) and categorized by system organ class using preferred terms. Treatment emergent AEs will be listed by study group. Treatment related AEs will be tabulated by study group and will be reported by incidence (both number of events and number of subjects) with respect to their intensity and relationship to the IP. Ophthalmoscopy findings will be summarized descriptively. IOP measurements, VA, and slit lamp biomicroscopy will be summarized as safety outcomes.

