Study Design	
A Phase I/IIa multicenter, double-masked, randomized, vehicle-controlled, dose-ranging study designed to evaluate the safety and preliminary efficacy of TRS01 eye drops ([REDACTED] compared to vehicle in subjects with post-surgical inflammation. Potential study participants will be asked to sign an informed consent document before the surgery and have to meet all preoperative inclusion/exclusion criteria. Following cataract surgery, subjects who are observed to have anterior chamber cells \geq grade 2 in the study eye on the Day 1 post-operative visit following a routine, uncomplicated cataract surgery will be eligible to be randomized to treatment (subjects who have $<$ grade 2 anterior chamber cells must be screen failed). Once it is determined that all eligibility criteria have been met, subjects will be enrolled and treated with one of three concentrations of TRS01 or vehicle in a 1:1:1:1 ratio. Approximately 60 eligible subjects will be enrolled in approximately five centers located in the United States (US) and France.
 
Study subjects will administer the randomly assigned treatment four times a day (QID) for 14 (± 1) days. All study subjects will return for examination on day 3, day 8 and day 15 post surgery. Day 15 visit will be

	
one day after the last day of treatment.
 
Clinical assessments will include subject-rated ocular pain assessment, slit lamp biomicroscopy, dilated ophthalmoscopy, intraocular pressure (IOP) measurement, snellen distance visual acuity (VA) by Pinhole Method.
 
[REDACTED]
 
[REDACTED]
 
The study visits schedule and assessments to be performed are described in Appendix 1.

Primary Safety Endpoints	
Assessment of ocular AEs: Changes that are expected due to uncomplicated cataract surgery will not be classified as AEs but will be recorded. AEs will be captured by verbatim term and coded using MedDRA.
 
Relevant clinical findings will also be recorded in the electronic case report form (eCRF) related to the following:
 
 1. Snellen distance VA by pinhole method 2. Slit lamp biomicroscopy 3. IOP measurement 4. Dilated ophthalmoscopy 5. Safety parameters include a change from baseline (1-day post-surgery) to each post-surgery visit in ocular signs such as: 
 o Conjunctival hyperemia o Corneal edema

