2 STUDY OBJECTIVES

The primary objective of this study is to evaluate the safety of TRS01 eye drops at concentrations of [REDACTED] w/v) compared to vehicle in subjects who have undergone uncomplicated cataract surgery.

The exploratory objective of the study is to assess the preliminary efficacy of TRS01 eye drops in reducing inflammation as compared to vehicle.

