3.1 SAFETY ENDPOINTS

The primary safety parameter in this study is the incidence and severity of treatment-emergent and treatment-related adverse events (AEs), both systemic and ocular events in subjects with post-cataract inflammation. Changes that are expected due to uncomplicated cataract surgery will not be classified as AEs but will be recorded.

1. Snellen distance visual acuity (VA) by pinhole method
2. Slit lamp biomicroscopy
3. IOP measurement
4. Dilated ophthalmoscopy
5. Change from baseline (1-day post-surgery) to each post-surgery visit in ocular signs:
 - Conjunctival hyperemia
 - Corneal Edema

All Relevant clinical findings will be recorded in the electronic case report form (eCRF).

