7 SAFETY AND EFFICACY VARIABLES

7.1 SAFETY VARIABLE

Incidence and severity of treatment-related AEs and SAEs, both systemic and ocular events.

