7.2.1 Adverse Events

Adverse events will be collected for subjects following signing of the ICF through the end of the study. The information will include at least a description of the event, onset date, and resolution date, as well as seriousness, severity and relation to study medication (as determined by the Investigator), location (right eye [OD], left eye [OS], both eyes [OU] or other), action taken, and outcome. All AEs will be coded using the Medical Dictionary for Regulatory Activities (MedDRA) dictionary, current version. Ocular and non-ocular AEs will be summarized separately.

Suspected adverse reactions (SARs), also known as adverse drug reactions or suspected adverse drug reactions, are AEs considered by the Investigator to be related to the study medication and included in the Investigator's Brochure.

An AE will be considered as an *ocular AE* if the Investigator selects 'OD', 'OS', or 'OU' for the AE eCRF field "Eye(s) affected".

Any AE that causes loss of vision of 15 or more letters (i.e., 3 lines) should be recorded as a serious adverse event (SAE). Examples include endophthalmitis, retinal vascular occlusion, retinal detachment involving the macula/fovea, etc. AEs that cause loss of 15 or more letters (i.e., 3 lines) that are expected to resolve should not be recorded as an SAE. Examples include corneal edema, corneal abrasion, cystoid macular edema or other conditions that are known to affect vision but expected to resolve and not results in a permanent impact on vision.

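### Section 9.1.2 states by-arm incidence only for treatment-related AEs; treatment-emergent AEs, also named in the primary safety parameter, get only a listing

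*Combined protocol and SAP*

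**What the plan says.** The planned AE outputs are in section 9.1.2: "Treatment emergent AEs will be listed by study group. Treatment related AEs will be tabulated by study group and will be reported by incidence". The sentence goes on to specify counts of events and of subjects, by intensity and relationship to the product.

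The endpoint is worded in three ways:

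- Section 3.1 makes the primary safety parameter "the incidence and severity of treatment-emergent and treatment-related adverse events (AEs), both systemic and ocular events".
- Section 7.1 has "Incidence and severity of treatment-related AEs and SAEs, both systemic and ocular events".
- The synopsis, under Primary Safety Endpoints, begins "Assessment of ocular AEs: Changes that are expected due to uncomplicated cataract surgery will not be classified as AEs but will be recorded".

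The primary objective in section 2 is safety "compared to vehicle in subjects who have undergone uncomplicated cataract surgery".

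Two more general statements bear on the point. Section 7.2.1 says "Ocular and non-ocular AEs will be summarized separately". Section 9.1 gives number and percent for categorical measures, promises listings of all data by treatment, and refers the analyses to a Statistical Analysis Plan.

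**The concern.** In adjacent sentences, section 9.1.2 gives one class of AE a listing and the other a table with incidence. A listing shows individual events; it is not a prespecified summary of how often they occur in each arm. As written, the comparison with vehicle on AE incidence rests on the related-only table.

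That table depends on a judgement about cause. Under section 7.3 an event readily put down to the operation is unrelated, and a probable relationship requires that the subject's condition does not easily explain the event. Every subject had surgery the day before the first dose, so an event compatible with both the surgery and the drop tends to leave the table. Randomization to vehicle is what allows arms to be compared without that judgement. What is at stake is whether the protocol commits to that comparison for its primary objective.

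**Working it through.** The plan has no figure of its own to reproduce here, and its sample-size section is redacted. The check is a comparison of texts.

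| Section | AE set | Measure or output | By arm? |
|---|---|---|---|
| Synopsis | Ocular AEs | Assessment | Not stated |
| 3.1 | Treatment-emergent and treatment-related | Incidence and severity | Not stated |
| 7.1 | Treatment-related AEs, and SAEs | Incidence and severity | Not stated |
| 7.2.1 | All AEs, split by ocular or not | Summary, measure unstated | Not stated |
| 9.1 | Categorical measures; AEs not named | Number and percent | Not stated |
| 9.1.2, first AE output | Treatment-emergent | Listing | Yes |
| 9.1.2, second AE output | Treatment-related | Incidence: events and subjects | Yes |

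**Step 1: is the table stated anywhere?** No row combines treatment-emergent, incidence and by arm. Because section 9.1 already lists all data by treatment, the listing sentence in 9.1.2 adds nothing, unless the word is loose usage for a table. Either way the text needs correcting.

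**Step 2: what does section 3.1 require?** There are two readings. If it names two sets of events, the treatment-emergent part has no stated by-arm incidence. If it means only events that are both emergent and related, the related-only table covers it, and section 7.1 leans that way. The synopsis fits neither cleanly.

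**Step 3: where does attribution enter?** It enters twice. First, changes regarded as normal after uncomplicated surgery are recorded but not counted as AEs (section 3.1, section 3.3 under Visit 3, Appendix 1 footnote 7). Second, what remains is graded for causality (sections 7.3 and 7.4), and the related-only table keeps the probable and definite events. An all-cause treatment-emergent table removes the second filter but not the first. Some recorded changes, such as corneal edema, reappear in the slit-lamp summaries. No by-arm summary is stated for the recorded changes as such.

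**Step 4: can treatment-emergent be derived?** The term is not defined. Section 7.2.1 says "Adverse events will be collected for subjects following signing of the ICF through the end of the study", and Appendix 1 has AE checks at screening, at surgery, and on Day 1 both before and after the first dose. Pre-dose events will therefore be in the database, and some may worsen on treatment. Section 7.4 records date and time of onset, so new events can be separated.

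**Step 5: size.** Inputs from section 3.3: about 60 subjects, allocated 1:1:1:1.

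- Subjects per arm: 60 / 4 = 15.
- One subject: 1 / 15 = 6.7 percentage points.
- Exact two-sided 95% upper limit for an arm with no events: 1 − 0.025^(1/15) = 21.8%.

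No AE rate or share of events judged related is given, so the gap between an all-cause and a related-only difference cannot be computed.

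**The case against.** The strongest reply is that the table may already be planned. Section 7.2.1 promises a summary of all AEs, section 9.1 supplies number and percent, and the Statistical Analysis Plan may specify the rest. The reference to relationship in 9.1.2 might also suggest that a wider table was meant. This stands in part. It rules out inferring that treatment-emergent incidence will never be reported. It does not fill the gap in the protocol, because neither general statement names study groups and treatment-emergent events together, and the subject of the 9.1.2 sentence is treatment-related AEs.

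Second, on the narrower reading of section 3.1 no part of the primary parameter is missing. This stands. What is firmly shown is that the three endpoint statements do not agree and that 9.1.2 matches only the narrower one.

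Third, no information is lost. Counts can be recovered from listings of about 60 subjects, and IOP, visual acuity, slit-lamp and ophthalmoscopy findings are summarized without a relatedness judgement. This also stands; the gap is in prespecification.

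A reader might go further and infer that causality is assigned with knowledge of treatment, because section 3.3.3 has unmasked site staff collect product-related AEs. The documents do not support that. The same section bars those staff from study assessments, section 4.3.1 masks investigators, and section 7.4 gives causality to the Principal Investigator. Nor do they support a claim that an all-cause table is free of attribution (step 3), or any stated amount by which a difference would shrink or grow.

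**Conclusion.** The point holds for the protocol text. Section 9.1.2 commits to by-arm incidence only for treatment-related AEs, while section 3.1 also names treatment-emergent AEs and section 2 calls for comparison with vehicle. The consequence is a missing prespecified summary and an unsettled endpoint definition, not lost data or a demonstrated bias. It should be fixed because it concerns the primary objective and costs little.

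The conclusion rests on two conditions: that section 3.1 means both sets of events, and that the Statistical Analysis Plan does not already contain the table. If the second fails, only the wording needs aligning; if the first fails, the endpoint statements still conflict. The only size the documents support is about 15 subjects per arm, with one subject worth 6.7 points, which is enough for description and not for testing.

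A minor side item: section 9.6 defines the Safety population as everyone randomized and ITT as those randomized and dosed, the reverse of what the labels imply, while 9.1.2 refers to all subjects. The first dose is supervised in the clinic after randomization, so few if any subjects should differ and the numerical effect should be very small.

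**What to change.** - **Section 9.1.2, AE table:** tabulate all treatment-emergent AEs by arm, including vehicle: number of events, number and percent of subjects, and maximum severity, with ocular and non-ocular AEs separate. Show treatment-related AEs as a subset.
- **Section 9.1.2, expected changes:** also summarize by arm the surgical changes that are recorded but not counted as AEs.
- **Definition:** define treatment-emergent as onset, or worsening of a pre-existing event, after the first dose. The protocol does not say how a change in severity is recorded, so state that convention too.
- **Endpoint wording:** use one statement of the primary safety parameter in the synopsis and sections 3.1 and 7.1.
- **Section 9.6 (minor):** define Safety as dosed subjects by treatment received and ITT as all randomized subjects, and point the population wording in 9.1.2 to Safety.

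The cost is wording changes and a few extra descriptive tables, essentially from fields already collected. Displayed AE counts will be higher in every arm, vehicle included.

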9.1.3 Analysis of Efficacy

Efficacy measures will be ACC and flare, as well as Subject-rated Ocular Pain Assessment.

Both Investigator-rated ACC and flare data will be assessed as a change from baseline (Visit 3/Day 1) on Days 3, 8 and 15 and a descriptive comparison of the active treatment groups to the vehicle group will be performed.

The Subject-rated Ocular Pain Assessment will be assessed as a change from baseline (Visit 3/Day1) on Days 3, 8 and 15 and a descriptive comparison of the active treatment groups to the vehicle groups will be performed.

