Tarsius Pharma, Ltd.
Clinical Protocol Tarsius 2020 Trial

Project: TRS01

Compound Number / Name: TRS01

Protocol Number: Tarsius 2020

Protocol Title: A Phase I/IIa Multicenter, Double-Masked, Randomized, Vehicle-controlled, Dose-ranging Study to Evaluate the Safety of TRS01 Eye Drops in Subjects with Post-surgical Inflammation.

Sponsor: Tarsius Pharma, Ltd.
[name]
[name]
[name]

Medical Monitor:

[REDACTED]
[REDACTED]
[REDACTED]
[REDACTED]

Issue Date: Original: 12November2019
Amendment 01: 06March2020

Approved:

11 March 2020

[REDACTED]
[REDACTED]
[REDACTED]
Date

Tarsius Pharma, Ltd.
Clinical Protocol Tarsius 2020 Trial
Investigator Signature Page

Project: TRS01

Compound Number / Name: TRS01

Protocol Number: Tarsius 2020

Protocol Title: A Phase I/IIa Multicenter, Double-Masked, Randomized, Vehicle-controlled, Dose-ranging Study to Evaluate the Safety of TRS01 Eye Drops in Subjects with Post-surgical Inflammation.

Sponsor: Tarsius Pharma, Ltd.
[name]
[name]
[name]

Issue Date: Original: 12November2019
Amendment 01: 06March2020

**Contact for Serious
Adverse Events:**

[REDACTED]

[REDACTED]

[REDACTED]

[REDACTED]

Investigator Name:

Investigator's Signature:

Date

SYNOPSIS

Sponsor	Tarsius Pharma Ltd.
Study Title	A Phase I/IIa Multicenter, Double-Masked, Randomized, Vehicle-controlled, Dose-ranging Study to Evaluate the Safety of TRS01 Eye Drops in Subjects with Post-surgical Inflammation.
Study Objective	The primary objective of the study is to investigate the safety of TRS01 [REDACTED] (w/v) eye drops compared to vehicle in subjects who have undergone cataract surgery.
Study Population	The study population will consist of male and female subjects, aged 18 or older, who have undergone routine uncomplicated cataract surgery and experience \geq grade 2 threshold level of ocular inflammation 1 day post-operatively.
Number of Subjects	Approximately 60 subjects that meet the selection criteria will be randomized for treatment following cataract surgery (one study eye). The number of subjects that will be screened to obtain 60 randomized subjects is estimated at approximately 100 subjects.
Investigational Product	TRS01-[REDACTED], TRS01-[REDACTED], and TRS01-[REDACTED] eye drops, or vehicle, will be supplied as investigational product.
Route and duration of administration	Study subjects will administer the randomly assigned treatment, as eye drops, four times a day (QID) for 2 weeks.

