4.3 RANDOMIZATION INCLUSION CRITERIA

To qualify for randomization at the Day 1 (Visit 3), a subject must:

1. Have undergone routine, uncomplicated cataract surgery (phacoemulsification or extracapsular extraction) with posterior chamber IOL implantation, not combined with any other surgery (including but not limited to use of iris retractors, capsular fixation ring or anterior capsule staining with dye). Specifically, have NOT had any cataract surgery complication such as a posterior capsular rupture, vitreous loss or significant iris damage.
2. Have an IOP of \leq 30 mmHg. Notes: Fluid release from the anterior chamber through the surgical incision is allowed (manual burping). The final IOP post release of fluid must be \leq 30 mmHg and will be recorded as the visit IOP value. Use of IOP lowering medications are allowed beginning on Day 0, with the exception of prostaglandins. IOP lowering eye drops should be dosed at least 30 minutes before investigational product dosing.
3. Have anterior chamber cells \geq grade 2.
4. Continue to meet inclusion/exclusion criteria with respect to current ocular and medical conditions and must not be taking prohibited medications (section 6.4).

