9.3 LEVEL OF SIGNIFICANCE

Level of significance to be outlined in the Statistical Analysis Plan.

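### Section 9.1.3 compares ACC, flare and pain only as raw change from Day 1; adding a difference adjusted for the Day 1 grade would guard against chance imbalance and usually sharpen the estimate

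*Combined protocol and SAP*

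**What the plan says.** Section 9.1.3 gives the only efficacy method in the supplied text. For cells and flare: "Both Investigator-rated ACC and flare data will be assessed as a change from baseline (Visit 3/Day 1) on Days 3, 8 and 15". For pain: "The Subject-rated Ocular Pain Assessment will be assessed as a change from baseline (Visit 3/Day1) on Days 3, 8 and 15". In each case the step that follows is descriptive; for cells and flare, "a descriptive comparison of the active treatment groups to the vehicle group will be performed". No covariate, model, estimator or interval is named.

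The Day 1 values needed for an adjustment are already collected. Section 5.1.3 puts the pain rating ahead of every other Day 1 assessment, and Section 8.1 puts the Day 1 slit-lamp examination, which covers cells and flare, before dosing.

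Entry restricts only one of the three measures. Section 4.3 requires subjects to "Have anterior chamber cells" of grade 2 or more. Flare (Section 8.1.2, graded 0 to 4) and pain (Section 8.1.3, graded 0 to 5) have no entry minimum.

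On status, Section 2 states: "The exploratory objective of the study is to assess the preliminary efficacy of TRS01 eye drops in reducing inflammation as compared to vehicle". Safety is the primary objective. Section 9.1 adds: "The statistical analyses will be performed in accordance with the Statistical Analysis Plan". Section 9.3 does the same for alpha: "Level of significance to be outlined in the Statistical Analysis Plan".

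**The concern.** Comparing raw change scores amounts to fixing the regression slope of follow-up on baseline at 1. In a resolving inflammation graded on short scales with a floor at 0, the true slope may well be lower. When it is, an arm that happens to start higher shows a larger fall for that reason alone, and the spread of the baseline adds noise to the difference.

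Three features of this design make that worth attention. The arms are small. All three doses share one vehicle arm, so a vehicle arm that starts high or low by chance moves all three differences in the same direction, which can be mistaken for a consistent drug effect or for its absence. And the only separation named for randomization (Section 4.3.1) is US sites from the French site; the Day 1 grade is not balanced by design.

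Flare and pain carry a further problem. A subject at grade 0 on Day 1 cannot improve on a change score, so an arm with more such subjects shows less mean improvement whatever the treatment does. With no test planned, the observed differences are the efficacy result, so their quality matters even in a descriptive analysis.

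**Working it through.** **Inputs.** From the documents: about 60 subjects randomized (Synopsis) in a 1:1:1:1 ratio (Section 3.3), so 60/4 = 15 per arm. Section 9.2 is redacted, so the plan offers no figure to reproduce. Assumed, because the documents give neither: the baseline-to-follow-up correlation r, and the ratio k = baseline SD / follow-up SD.

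**Formulas**, in units of the follow-up variance, with one ANCOVA pooled over four arms (N = 60):

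- Change score: k² + 1 − 2rk, which is 2(1 − r) when k = 1.
- ANCOVA: (1 − r²)(1 + 1/(N − 6)) = (1 − r²) × 55/54. The last factor is the cost of estimating the slope.
- Slope of follow-up on baseline: r/k. A baseline gap d between two arms shifts the change-score difference by (r/k − 1)d.
- Standard error (SE) of a two-arm difference: the square root of the variance above times 2/15. One SE of a baseline gap is √(2/15) = 0.365 baseline SD.

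**Equal SDs (k = 1).** Example at r = 0.3: change 2 × 0.7 = 1.40; ANCOVA 0.91 × 55/54 = 0.927; ratio 1.51.

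| r | Variance ratio, change / ANCOVA | SE, change | SE, ANCOVA | Shift in change-score difference from a 1-SE baseline gap |
|---|---|---|---|---|
| 0.3 | 1.51 | 0.432 | 0.352 | −0.256 SD |
| 0.5 | 1.31 | 0.365 | 0.319 | −0.183 SD |
| 0.7 | 1.16 | 0.283 | 0.263 | −0.110 SD |

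The share of the imbalance carried over is 1 − r: 70%, 50% and 30%. ANCOVA removes it, to the extent that the linear slope is right.

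**Unequal SDs.** Variance ratio, change / ANCOVA:

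| k | r = 0.3 | r = 0.5 | r = 0.7 |
|---|---|---|---|
| 0.5 | 1.02 | 0.98 | 1.06 |
| 0.75 | 1.20 | 1.06 | 0.99 |
| 1.5 | 2.54 | 2.29 | 2.21 |

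A value of k near 0.5 is plausible for ACC, because entry removes grades below 2. At k = 0.5 and r = 0.5 the slope is exactly 1: nothing is carried over, and ANCOVA is about 2% worse because of its one degree of freedom.

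**Ordinal grades.** Rounded 0-4 grades with a floor at 0 were simulated with 15 per arm, slopes of 0.3, 0.6 and 0.9, and assumed grade distributions. The variance ratio was 0.99 to 1.39 for ACC-like data (baseline grades 2 to 4) and 1.03 to 2.19 for flare-like data with no entry limit. The change-score difference correlated with the baseline gap at −0.11 to −0.54 (ACC-like) and −0.22 to −0.74 (flare-like), against about 0 for ANCOVA. The mean estimated effects of the two methods agreed to within about 0.005 grade, so neither is biased relative to the other over repeated randomizations.

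**How often imbalance arises.** With four arms of 15 and normal baselines (assumed), at least one of the three dose-vehicle baseline gaps exceeds 0.365 SD in about 62% of trials and 0.5 SD in about 38%. Because the vehicle mean enters every difference, any two of these gaps have correlation (1/15)/(2/15) = 0.5.

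**The case against.** The strongest reply is that nothing planned is damaged. Efficacy is exploratory, the comparison is descriptive, and no test or interval is specified, so lost precision alters no stated conclusion. That stands, and it limits how serious the point is. It does not make the raw change the better summary of the same data.

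A reader might infer that the sponsor has decided against adjustment. The documents do not show that. The protocol is silent and defers to an analysis plan not supplied, which may already name the Day 1 grade as a covariate.

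A reader might also infer that the efficacy differences are biased, or that every one of them loses precision. Neither follows. The change score is unbiased over randomization; only the interpretation of one particular imbalanced trial suffers. For ACC the loss can be nil.

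Larger gains, such as the ratios above 2 at k = 1.5, require flare or pain to be bunched near the floor by Day 15. The documents do not establish this. Section 1 puts resolution without treatment at 15-28% of patients, so follow-up grades under vehicle could be as spread out as at baseline.

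It is tempting to add that dose selection is compromised. The study is called dose-ranging, but no section says that these differences will choose a dose.

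Two technical objections also stand. Linear ANCOVA does not cure the floor at grade 0, which strains its common-slope assumption. And under Section 6.2 rescued subjects stop study medication, stay in the study and count as treatment failures, so a model of mean grade needs a stated rule for their later values. Finally, Section 9.1 lists all data by treatment, subject and visit, so imbalance could be seen, though not adjusted for.

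**Conclusion.** The point holds as a worthwhile, low-cost improvement, not as an error that invalidates an analysis. The supplied text specifies raw change alone and leaves unused a covariate that the trial already collects. With about 15 per arm, part of any chance Day 1 imbalance passes into the dose-vehicle differences: 30% to 70% of it for equal SDs and r from 0.7 to 0.3. Under the same assumptions the change-score variance is about 16% to 51% larger than that of ANCOVA.

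The direction is secure for flare and pain unless the slope is close to 1. For ACC the gain may be about zero, with a possible loss of about 2%. The sizes rest on r, k and the grade distributions, none of which is in the documents. The conclusion concerns precision and reading conditional on the observed baseline. It does not concern average bias, a planned test, or a documented decision to leave baseline out.

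**What to change.** In Section 9.1.3 or the Statistical Analysis Plan, unless the latter already does so:

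- For each measure at Days 3, 8 and 15, also report each dose-minus-vehicle difference adjusted for the Day 1 grade, from ANCOVA or a repeated-measures model, with a 95% confidence interval labelled exploratory. Use an ordinal model as a sensitivity analysis.
- Keep raw change from Day 1 as a supporting summary.
- Tabulate Day 1 grades of cells, flare and pain by arm.
- Show the number of subjects at grade 0 by visit and arm for pain and flare, since the adjusted mean does not resolve the floor.
- State how grades recorded after rescue enter the model, consistently with the treatment-failure rule in Section 6.2.

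The cost is one degree of freedom, some plan text and a little more analysis work. Three doses, three visits and three measures give 3 × 3 × 3 = 27 intervals, which is why the exploratory label matters. No new assessments or subjects are needed.
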